14.1 Definition of the End of Study

This is defined as the last data entry point.

14.2 Annual Progress Reports

The Chief Investigator will prepare the APR for non CTIMPs. It will be reviewed by the Sponsor and sent to the REC by the CI within 30 days of the anniversary date on which the favourable opinion was given by the Ethics Committee, and annually until the study is declared ended.

15 Finance

Funding provided by the OAA/NIAA Large project grant 2016 awarded to the principal applicant [name].

16 Insurance and indemnity

NHS bodies are liable for clinical negligence and other negligent harm to individuals covered by their duty of care. NHS Institutions employing researchers are liable for negligent harm caused by the design of studies they initiate.

17 IP and development policy

Unless otherwise specified in agreements, the following guidelines shall apply: all Intellectual Property Rights and Know How (IP) related to the Protocol and the study are and shall remain the property of the Sponsor excluding:

- 1) pre-existing IP related to clinical procedures of any Hospital.
- 2) pre-existing IP related to analytical procedures of any external laboratory.

All contributors:

shall assign their rights in relation to all Intellectual Property Rights and all Know How, not excluded above to the Sponsor and at the request and expense of the Sponsor, shall execute all such documents and do all such other acts as the Sponsor may reasonably require in order to vest fully and effectively all such Intellectual Property Rights and Know How in the Sponsor or its nominee.

shall promptly disclose to the Sponsor any Know How generated pursuant to this Protocol and not excluded above and undertake to treat such Know How as confidential information jointly owned between it and the Sponsor.

Nothing in this section shall be construed so as to prevent or hinder a medical professional from using Know How gained during the performance of the study in the furtherance of its normal business activities, to the extent such use does not result in the disclosure or misuse of confidential information or the infringement of any Intellectual Property Right of the Sponsor.

18 Publication policy

Publication: “Any activity that discloses, outside of the circle of study investigators, any final or interim data or results of the study, or any details of the study methodology that have not been made public by the Sponsor including, for example, presentations at symposia, national or regional professional meetings, publications in journals, theses or dissertations.”

All scientific contributors to the study have a responsibility to ensure that results of scientific interest arising from the study are appropriately published and disseminated. The Sponsor has a firm commitment to publish the results of the study in a transparent and unbiased manner without consideration for commercial objectives.

To maximise the impact and scientific validity of the study, data shall be consolidated over the duration of the study, reviewed internally among all investigators and not be submitted for publication prematurely. Lead in any publications arising from the study shall lie with the Sponsor in the first instance.

The DREAMY website will be used to provide free online access to study information. All publications will include “PLAN” as an authorship group, with PIs and Local Investigators individually named as collaborators. The CI and research development team will use lecture and webcast opportunities to publicise study results to healthcare professionals in anaesthesia,

obstetric surgery and critical care. Our lay representative will lead dissemination of important study findings to the public.

19 Statement of compliance

The study will be conducted in compliance with the protocol, Sponsor's Standard Operating Procedures (SOPs), GCP and the applicable regulatory requirement(s).

The study conduct shall comply with all relevant laws of the EU if directly applicable or of direct effect and all relevant laws and statutes of the UK country in which the study site is located including but not limited to, the Human Rights Act 1998, the Data Protection Act 1998, the Human Medicines Regulations 2012, ICH GCP, the World Medical Association Declaration of Helsinki entitled 'Ethical Principles for Medical Research Involving Human Subjects' (2008 Version), the NHS Research Governance Framework for Health and Social Care (Version 2, April 2005).

Appendix 1. Protocol amendment / Revision history

| Protocol Version and Date | New text |
|---------------------------|------------------------------|
| Protocol 1.0 | Version submitted to HRA/REC |
| | |
| | |
| | |
| | |

Appendix 2. Modified Brice questions

1. What is the last thing you remember before going to sleep?

- | | | | |
|------------------------------------|--------------------------|---------------------------|--------------------------|
| Being in the pre-op area |  | Seeing the operating room |  |
| Being with family |  | Hearing voices |  |
| Feeling mask on face |  | Smell of gas |  |
| Burning or stinging in the IV line |  | | |
| Other (Free Text): | | | |

2. What is the first thing you remember after waking up?

- | | | | |
|---------------------------|--------------------------|----------------------------|--------------------------|
| Hearing voices |  | Feeling breathing tube |  |
| Feeling mask on face |  | Feeling pain |  |
| Seeing the operating room |  | Being in the recovery room |  |
| Being with family |  | Being in intensive care |  |
| Nothing |  | | |
| Other (Free Text): | | | |

3. Do you remember anything between going to sleep and waking up?

- | | | | |
|------------------------------|--------------------------|-------------------------------|--------------------------|
| No: |  | | |
| Yes: Hearing voices |  | Hearing events of the surgery |  |
| Unable to move or breathe |  | Anxiety/stress |  |
| Feeling pain |  | Sensation of breathing tube |  |
| Feeling surgery without pain |  | | |
| Other (Free Text): | | | |

4. Did you dream during your procedure?

- | | | | |
|-------------------------|--------------------------|------|--------------------------|
| No: |  | Yes: |  |
| What about (Free Text): | | | |

5. Were your dreams disturbing to you?

- | | | | |
|-----|--------------------------|------|--------------------------|
| No: |  | Yes: |  |
|-----|--------------------------|------|--------------------------|

6. What was the worst thing about your operation?

- | | | | |
|------------------|--------------------------|------------------------|--------------------------|
| Anxiety |  | Pain |  |
| Recovery process |  | Functional limitations |  |
| Awareness |  | | |

Appendix 3. Anaesthetic episode data collection parameters

Age: _____ years

Parity: G____P____

Procedure:

LSCS

MROP

EUA

Other _____

Urgency of surgery/LSCS:

Emergency/Cat. 1

Urgent/Cat. 2

Expedited/Cat. 3

Elective/Cat. 4

ASA: 1 2 3 4 5

Booking BMI (kg/m²): <18.5 18.5-24.9 25-29.9
 30-34.9 >35

Anaesthesia times: Start ____hh: ____mm Finish ____hh: ____mm

Induction agents:

Thiopentone Dose _____mg

Propofol Dose _____mg

Fentanyl Dose _____mcg

Alfentanil Dose _____mcg

Other (e.g. Ketamine, Remifentanil):

_____ Dose _____mg/mcg

De novo or conversion to GA: De novo Conversion

Indication for GA:

Clinical urgency Failed regional block

Maternal preference High spinal

Regional block contraindicated

Other: _____

Rapid sequence induction: Yes No

Maintenance agent(s): tick all that apply

Sevoflurane Isoflurane

Desflurane Nitrous oxide

Propofol (TIVA) Remifentanil (TIVA)

MAC: Lowest _____ Highest _____ Estimated median _____

Primary airway device:

Cuffed ETT Igel

LMA Supreme LMA

If a supraglottic airway device used, was this because of difficult intubation?:

Yes No

Grade of laryngoscopy: 1 2a 2b 3 4

Difficult intubation: Yes No

Please provide additional information where intubation was difficult, for example: How many attempts, use of bougie, change of laryngoscope:

Local/regional anaesthesia:

Spinal Epidural

CSE TAP block

Rectus sheath block

Neuromuscular blockade:

Suxamethonium Rocuronium

Atracurium Other _____

Nerve stimulator use: Yes No

Reversal use: Neostigmine/glycopyrolate Sugammadex

Depth of anaesthesia monitor use: BIS Other _____

Most senior anaesthetist present:

ST3-4 ST5-7

Associate specialist Staff grade

Consultant CT1-2

Location of extubation:

Theatre Critical care (Level 2 or 3)

Recovery

Post operative destination:

Delivery suite/post natal ward Critical care (Level 2 or 3)

Delivery suite HDU (midwifery-led) Other: _____

Estimated blood loss:

0-499ml 500-999ml

1000-1999ml >2000ml

Appendix 4. Structured follow-up questions for patients with Suspected AAGA

Part 1. When you completed our first questionnaire, you mentioned that you remembered something between going to sleep at the beginning of your surgery and waking at the end of your surgery. Do you still have memories of events that occurred during your surgery?

Yes No

A. Can you describe when or how you started remembering it?

Recalled on waking

Memory was there all the time but it took a while to realise what it was a memory of

Memory emerged gradually/gradually pieced together

Something triggered the memory

If something triggered the memory, then do you know what that was?

B. When you remembered, did you tell someone or plan to tell someone about your experience?

C. If so, who did you tell? Why did you tell that particular person?

D. If not, why not?

E. If you told someone, how did they react?

Part 2. What do you remember?

Can you describe in your own words what you remember, what you thought and how you felt?

A. Did you hear anything? (What?)

Voices (gender) Specific words

Music

Other (Free Text):

B. How did you feel?

Calm Afraid

Interested Helpless

Reassured Trapped

Confused Distressed

Detached Surprised

Other (Free Text):

C. What thoughts, if any, went through your mind at the time?

D. If you were you afraid or distressed at the time, what affected you most:

Unexpectedness of the awareness An experience of pain

An experience of paralysis or inability to move

An inability to communicate to those around you

Fear that something had gone wrong

Something else (please specify):

E. Did you experience any sensations?

Warmth Pressure

Cold Pain

Other (Free Text):

F. Did you try to move or speak? If yes, could you?

G. Did you try to open your eyes? If yes, could you?

H. What was your breathing like?

Normal Fast

Laboured Unable to breath

Other (Free Text):

I. Did you see anything?

Light Colours

Shapes Specific image

Other (Free Text):

Part 3. Did you go to the intensive care unit (may also be called the critical care unit or intensive treatment unit) after your surgery? If yes, did you still have the breathing tube in?

Did not go to intensive care Did go to intensive care

Remember having a breathing tube in?: Yes No Not applicable

B. When do you think your awareness experience occurred?

Before the start of the surgery During the surgery

When waking up from the surgery

C. Do you think your awareness experience took place in the operating room or in the intensive care unit or both? Why do you think this?

Operating room During the surgery

D. How long do you think the awareness experience lasted?

Part 4. Do memories of the event still trouble you now?

A. Do you sometimes feel that you are reliving the experience, or that it is happening to you again?

B. Do you have dreams or nightmares about the experience?

C. Do you feel anxious or fearful about something that you were not anxious about before?

D. Do you feel unusually upset or emotionally numb?

E. Have you felt any negative emotions because of your memories?

Fear Helplessness

Anger Frustration

Other (Free Text):

F. Do you avoid any situations as a result of your experiences?

G. Have your social life or relationships been affected?

H. Do you have problems sleeping? Have these changed since your experience?

I. Have you spoken to a health counsellor, GP, psychologist or other professional about these experiences?

Part 4. How would you feel about having an anaesthetic in the future?

A. Would you like to speak to a professional about your experiences?

B. Is it all right with you if we contact you again to talk to you about your experiences?

Yes, you may contact me again

No, I would prefer NOT to be contacted

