The default follow up methodology for encounters led by the DREAMY Research Team will be telephone structured interview schedules. At the start of the study equivalent written/email questionnaire forms of the interview questions will be provided to maximise follow up data collection. Alignment of responses between different data collection formats will be maximised by using interview schedules structured identically to paper questionnaires and presenting both with simple, equivalent contextual information. During interim analysis if a response format (i.e. telephone, face-to-face or written) is found to be infrequently selected by participants, then this choice may later be removed to further maximise data concordance.

"Brice positive" respondents will receive targeted questions on risk factors for post-natal PTSD ([Appendix 6](#)) during 30 day follow up and be offered the PCL-5 PTSD checklist ([Appendix 5](#)) at 30 days, 3, 6, 9 and 12 months following the index anaesthetic episode. The questions and checklist will be administered by telephone (or via email, at participant request) by the DREAMY Research Team.

An extended questionnaire for "Brice positive" participants will also be undertaken during the 3 month PTSD follow up episode ([Appendix 7](#)). This questionnaire is designed to explore the nature of local clinical follow received by patients and how the AAGA episode has impacted on attitudes towards future anaesthetics and post-natal experience.

Anaesthetic episode data collection will be conducted retrospectively by the anaesthetic Local Investigators from patient notes and anaesthetic records after each participant has provided written consent for study involvement. Data collected on the anaesthetic episode is detailed in [Appendix 3](#) and includes: age of patient, parity, procedure, urgency of surgery/LSCS, ASA status, booking BMI, anaesthesia start/finish time, induction agents (and doses), de novo or conversion to GA, indication for GA, rapid sequence induction, maintenance agent, nitrous oxide use, MAC, (lowest, highest, estimated median), primary airway device, difficult intubation, grade of laryngoscopy, local/regional anaesthesia, neuromuscular blockade, nerve stimulator use, reversal use, depth of anaesthesia monitor use, most senior anaesthetist present, location of extubation, post op destination, estimated blood loss.

1. 0h = Time of GA for obstetric indication surgery.

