9.2 Modified Brice Questionnaire

Screening for AAGA is being assessed in this study using the Brice Questionnaire, which has been adapted from the original published form [Brice 1970] in accordance with common usage [Avidan 2011]. Questions used in the modified Brice questionnaire are available in [Appendix 2](#). Initial screening will be done by local investigator teams, who will be invited to contact the CI or DREAMY Research Team members with any queries regarding Brice response classification. All Local Investigators will be provided with training to ensure that responses are assessed in a consistent manner. In assessing whether a response should be assigned as “Brice positive”, investigators will be instructed to focus on memories of events that could occur only in the operating room during the anaesthetic and surgical periods. Participant reports of memories during the period between "going to sleep" and "waking up" will be taken as “Yes” answers to any of Q3, Q4 or Q5 or “Awareness” to Q6. Any such responses, indicating possible AAGA, require the Local Investigator to follow the Suspected AAGA follow up protocol (see [section 9.3](#)). If an investigator is in any doubt about whether the Brice Questionnaire responses constitute a possible AAGA event, then the responses should be discussed with the local PI and/or CI.

Final classification of Brice responses will be performed by the same expert panel responsible for making final AAGA classification decisions.

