Appendix 7. AAGA Extended follow up questions

Part 1. Have you had any further memories, recollections or thoughts about your experience during the anaesthetic?

Part 2. Please think back to the time when your first remembered having an awareness experience.

Did you want to speak to a member of the anaesthetic team at your local hospital about your awareness experience?

Yes No

Was the opportunity made available for you to speak a member of the anaesthetic team at your local hospital?

Face to face meeting:

Yes No

Telephone discussion:

Yes No

Other _____

If you had a meeting, then when did this take place?

Within 24 hours of reporting having awareness

1-2 days after reporting awareness

3-7 days after reporting awareness

>7 days after reporting awareness

Before hospital discharge After hospital discharge

Did you feel that the local team listened to your story and experience?

Yes No

Did anyone apologise or express regret to you about your experience?

Yes No

Who else have you seen as part of your follow up for your awareness experience?

Please rank how helpful you found each specialist, relative to others (please rank as 1 the specialist that offered you the most emotional or practical support to enable you to understand and come to terms with your experience).

Anaesthetist How many meetings? _____ Rank _____

Clinical Psychologist How many meetings? _____ Rank _____

Psychiatrist How many meetings? _____ Rank _____

GP How many meetings? _____ Rank _____

Counsellor How many meetings? _____ Rank _____

Other _____ How many meetings? _____ Rank _____

If you haven't already then would you like to speak to any of the following:

Clinical Psychologist Psychiatrist
 GP Counsellor

Did you receive any feedback regarding any local investigation that may have taken place to find the cause of your awareness incident?

Yes No

How would you grade the quality of support you received following reporting your awareness event?

| | | | | |
|------------------|-------------|-----------------|-------------|------------------|
| Very poor (0) | Poor (1) | Moderate (2) | Good (3) | Very good (4) |
|------------------|-------------|-----------------|-------------|------------------|

What aspects of your post-awareness support did you find particularly helpful?

What aspects of your post-awareness support did you not find helpful?

How might you improve post-awareness support for other patients?

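### The Suspected AAGA interview opens by treating every flagged woman as having reported recall, although a dream or a Q6 tick alone is enough to flag her, and so can lead the account the panel classifies

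*Protocol*

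**What the plan says.** **Trigger (Section 9.2).** A woman is treated as possibly aware if she gives Yes "answers to any of Q3, Q4 or Q5", or chooses awareness at Q6. Such responses "require the Local Investigator to follow the Suspected AAGA follow up protocol".

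**The items (Appendix 2).** Q3 asks: "Do you remember anything between going to sleep and waking up". Q4 asks only whether she dreamed, and Q5 whether the dreams disturbed her. Q6 is a tick list of the worst aspects of the operation, with awareness as one box.

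**The interview (Appendix 4).** Part 1 has a single opening with no conditions: "When you completed our first questionnaire, you mentioned that you remembered something between going to sleep at the beginning of your surgery". The next sentence is "Do you still have memories of events that occurred during your surgery", answered Yes or No. Part 1A is a tick list on how the memory came back. Part 2 then asks for an account in her own words, followed by lists of sounds, feelings and sensations. Part 3B asks when the awareness took place and offers before surgery, during it, or on waking. Parts 3C and 3D ask where it happened and how long it lasted.

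**Use of the answers (Section 6.3).** At least four assessors independently evaluate all responses and grade events by consensus. AAGA classification follows review of the follow-up responses, and its agreement with classification on the Brice answers alone is to be reported.

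**The concern.** The trigger is wider than the script allows for. The opening restates Q3 as something the woman has already said, yet she may have been flagged with Q3 = No. In a study of memory, telling a respondent what she earlier reported, and then asking whether she still has it, is a leading sequence. The suggestion runs towards recall.

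Three results depend on the answers:

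- the panel's AAGA classification after the interview, and any event proportion calculated from it;
- the agreement between that classification and Brice-only status, which means less if the second step tells women what they said at the first;
- the AAGA and non-AAGA groups whose PCL-5 results are compared (Sections 12.1.2 and 12.2.3).

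**Working it through.** There is no figure to reproduce. The check sets the trigger, the items and the script side by side.

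**Step 1. Who is sent to the interview, and does the opening fit her?**

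| Brice answers | Interview required? (9.2) | Did she say what the opening attributes to her? | Does the 'still' question fit? |
|---|---|---|---|
| Q3 Yes | Yes | Yes | Yes, it follows from her own report |
| Q3 No, Q4 Yes (with or without Q5) | Yes | Only if a dream counts as remembering something | No, she reported a dream and not surgical events |
| Q3 No, Q4 No, Q6 awareness | Yes | Not in those terms; she ticked a box | No, she described no events |

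Q5 adds little as a separate route, because it asks about dreams already reported at Q4. The last two rows carry the point.

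**Step 2. Can she correct the premise?** Part 1 allows No. After the word 'still', No could mean that she never had such a memory or that it has gone. The panel would read these differently, but the form records them alike.

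**Step 3. What follows a No?** Appendix 4 prints no skip. Part 1A, on how the memory arose, comes before the own-words account in Part 2. Part 3B has no option for a dream or for no awareness, and Parts 3C and 3D keep the same premise. A woman who only dreamed has no accurate box to tick at 3B.

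**Step 4. Does it reach a result?** Yes, through Section 6.3, where AAGA classification follows review of these responses.

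**Step 5. How large is it?** The number of classifications shifted would be n × d × s × c, where

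- n is the number of women enrolled;
- d is the share flagged with Q3 = No;
- s is the share of those whose account moves towards recall because of the wording;
- c is the share of those accounts that the panel confirms.

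The protocol gives a target n of 2250 and nothing on d, s or c. The product cannot be computed.

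**The case against.** **What stands against the point.**

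- Section 9.2 itself treats a Yes at Q4 or Q5, or awareness at Q6, as a report of memory between going to sleep and waking. A dreamer did, on that rule, remember something, so the opening sentence alone is imprecise for her rather than false. This does not rescue the next sentence, which asks about events during surgery.
- Section 9.2 also tells investigators to focus on memories of events that could occur only in the operating room. This may keep some dreams out, but the follow-up requirement is still written for any such response.
- Part 2 invites her own words before its sensory lists, and the panel can see that Q3 was No. Both limit the bias without removing it.
- Reporting the agreement of the two classifications gives some sight of a shift. It cannot tell a memory confirmed from a memory suggested.

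**Stronger readings that the documents do not support.**

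- *Women first flagged at 24-48 hours or day 30 are also misdescribed.* Section 9.3 calls this interview secondary, so the first questionnaire can naturally mean the Brice form at any repetition.
- *The script is bound to be read as printed.* Section 6.2 aligns formats by "using interview schedules structured identically to paper questionnaires". That matches the formats to each other and does not make Appendix 4 a verbatim script. Section 9.3 says only that the interview is based on its questions, and working forms may carry skips that are not shown.
- *Appendix 7 inflates incidence in the same way.* Its phrase "remembered having an awareness experience" presumes awareness, but that form covers support and attitudes at 3 months and not case classification.
- *A few suggested cases would match the whole count expected under the first hypothesis, 2250/660 = 3.4.* That is a count of Brice positivity (Section 12.2.2), which Section 6.3 bases on Brice responses alone. These women are flagged before the interview, so it does not add them to that count. Section 9.2 gives the final Brice classification to the same panel, which leaves an indirect route at most. Assumed dream-only rates of 1% to 10% and acceptance of 1% to 5% give 2250 × 0.01 × 0.01 = 0.2 to 2250 × 0.10 × 0.05 = 11.3 accounts. Those rates are not in the documents, and counting every such account as a case assumes that the panel confirms all of them.

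**Conclusion.** The point holds for women with Q3 = No who were flagged by a dream or by Q6. For them the opening of Appendix 4 turns the answer they gave into recall of surgical events, and the form gives no clean way to say otherwise. The likely direction is towards recall in the post-interview AAGA classification, its agreement with Brice-only status, and the PTSD groups built on it.

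That the wording leads is an inference from the text, and its effect has not been measured. The size is unknown and is limited by the panel's sight of the Brice answers. The conclusion assumes that the working form follows Appendix 4 closely. If it already branches by trigger, the point reduces to bringing the appendix into line with it.

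The change is worth making because it is cheap and because an account, once led, cannot be taken again unled.

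**What to change.** Amend Appendix 4 before use:

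1. Replace the Part 1 opening with a neutral prompt that asserts no earlier answer, for example: *Please tell us in your own words anything you remember from just before, during and just after your anaesthetic.* Alternatively, branch the opening on the item that triggered follow-up.
2. Move the existing own-words account from Part 2 ahead of the Part 1A tick list.
3. Add options for a dream and for no awareness to Part 3B.
4. Print a skip past the awareness-specific items when no memory is reported.

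The cost is the rewording of one form and a minor amendment, with no extra contacts. There is a slight loss of comparability with the earlier trial's instrument from which the questions were adapted.
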